4.0 STUDY PROCEDURES

4.1. Informed Consent and Baseline Survey

Potentially eligible patients will be approached by study team members for verbal informed consent, either by mail/ email, during clinic visits, or by phone. Patients will receive a study packet that will contain an invitation letter, interest postcard, return envelope, and informed consent document. Patients will be randomized into one of three arms immediately after enrollment. Arm 1 is usual care, Arm 2 is return of results only in the HOPE-Genomics tool, and Arm 3 is return of results plus pretest education in the HOPE-Genomics tool.

Arm 1 patients will receive

a pamphlet (20430 Educational Brochure in iRIS) about WES after they enroll. Their clinician will return their genomics test results in a typical manner, without the assistance of the HOPE-Genomics tool.

Arm 2 patients will receive their genomics test results both from their clinician and from the HOPE-Genomics tool but will only view the tool after their results are available. Arm 3 patients will view the HOPE-Genomics tool (containing educational content) before their sequencing results are available. These patients will also receive their genomics test results both from their clinician and from the HOPE-Genomics tool. After completing all study surveys at 9 months post results disclosure, participants in Arm 1 (usual care), will receive access to the HOPE-Genomics tool, which will contain both the educational information and the personalized genomics results.

Table 1: Outcome and covariate data collection

			Patient surveys			MRA
	Baseline	Pre-edu. survey	T1	T2	T3	
Genetic Care outcomes						
MD recommendations						
Screening, surgery, meds			X	X	X	X
Referrals GC, specialists			X	X	X	X
Cascade testing			X	X	X	X
Patient utilization/behavior						
Screening, surgery, meds			X	X	X	X
Consult GC, specialists			X	X	X	X
Inform family members			X	X	X	
Cascade testing			X	X	X	
Patient-centered outcomes						
Recall of results	X		X	X	X	X
Understanding of results			X	X	X	
Genomic knowledge	X	X	X	X		
Engagement in care			X	X	X	
Information seeking				X		
Psychosocial impact	X		X	X	X	
Follow up outcomes						
HOPE-Genomics usability			X	X		
Satisfaction with MD-patient communication and care			X	X		
Covariates						
Socio-demographics	X					X
Clinical information						X
Other (e.g., health literacy)	X					X

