4.6 Medical Record Abstraction

Throughout the study, study staff will perform a limited medical record abstraction of consented participants. Primary outcome data will include high-risk screening, surgery, chemoprevention, targeted therapies, genetic counseling, informing family members, and cascade testing. Covariate data will include sociodemographic information, cancer information, germline and somatic genomic biomarker testing, and dates and types of treatments for cancer. Additional outcomes are detailed in Table 1.

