6.0 DATA ANALYSIS

As noted in Section 4.0, we are administering the survey items in order to help with item reduction for the trial. We will generate descriptive statistics (e.g., distributions, means) in order to evaluate for ceiling and floor effects. An amended survey will be submitted prior to administration.

Primary outcome (i.e., patient knowledge, recall rates) will be assessed at the 10-day post-disclosure timepoint.

We will be using MRA and survey data to evaluate if participants received contextual guideline-concordant care. This will involve review of receipt of prophylactic surgery, chemoprevention, targeted therapy for germline mutations, consultation with genetic counseling/ genetic specialists, informing family members, and family member cascade testing. To generate concordance scores for patients already on active therapy, patients will be asked about their current and/or planned cancer treatment at baseline and at each follow-up timepoint in the study (i.e., chemotherapy, radiation therapy, cancer-directed surgery, hormone therapy, immunotherapy, and targeted therapy). Patients will be considered as being contextually guideline-concordant if they receive at least 75% of the recommended guidelines. In sensitivity analyses, we will vary the cutoff for guideline- concordance between 50% and 100%. Survey data will also be used to evaluate usability of the HOPE-Genomics application, the psychosocial impact of using the tool, engagement in care, genetic knowledge, and understanding of genomic test results

6.1 Sample Size and Accrual Rate:

We plan to anchor our cohort on patients with somatic testing. We expect to accrue 465 patients: 155 per each arm. We assume that there will be a 10% attrition rate among accrued patients, leaving us with a final analytical sample of 390 patients. For the first 3 months, we assume that 17 patients are enrolled each month, during which time we will evaluate and optimize study processes. After this we will increase monthly accrual to 35 patients. We expect to be complete with accrual in 16 months. Patient participation will be approximately 7 months consisting of baseline pre-testing followed by genetic testing/results disclosure and then post-testing. The estimated total study time including analysis will be 26 months.

6.2 Statistical Analysis Plan:

The study data will consist of three main areas:

- 1) patient knowledge testing and clinical care recommendations via survey-based questions

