- 2) patient demographic information collected via the electronic medical record (EMR); and
- 3) patient clinical and treatment information collected via the EMR.

This information will be used to evaluate outcomes, predictors and adjust for covariates.

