We will test if the use of HOPE-Genomics will result in higher rates of uptake of evidence-based genetically guided care (e.g., patient receipt of guideline concordant care, cascade testing) than usual care: Our primary goal will be to assess whether or not the uptake of contextual guideline-concordant care differs between the two arms. The primary objective is to test the null hypothesis of no intervention effect on the outcome. We expect that patients in the intervention arm will have higher rate of uptake of contextual guideline-guided care than patients in the control arm. A two-sided Type I error of 0.05 will be used for all statistical tests. We will consider two-sided p-value less than 0.05 as a statistically significant. Patients will be considered concordant ($Y=1$) if they undergo a predetermined percentage of genetically guided care and discordant ($Y=0$) otherwise. Using an intention-to-treat analysis, the proportion of concordant patients will be modeled using the logistic regression approach for binary outcome (PROC LOGISTIC in SAS [Cary, N.C.]). We will use compound symmetry and unstructured working correlation matrix to account for correlation between patients within the same physician. The odds ratio of the concordant patients between the intervention and control arms will be calculated using the group coefficient in the Logistic model. The significance of the coefficient will be tested to determine treatment group difference. In addition, we will use Kauermann and Carroll (KC) correction for robust SEs if the number of physicians is small.¹¹ To evaluate the success of randomization, we will test the differences in characteristics of physicians and patients between the two arms. The Logistic model will include statistically significant characteristics as covariates. Logistic will also be used to model the percentage of the rate of uptake of the genetically guided care per patient, treated as a binomial variable, and include the within-physician correlation, to test for treatment group difference.

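### Aim 2 covariates are chosen by between-arm significance tests, so the model performs like no adjustment and chance imbalance decides which odds ratio is reported

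*Combined protocol and SAP*

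**What the plan says.** Allocation is by individual patient (Section 4.1): "Patients will be randomized into one of three arms immediately after enrollment".

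For Aim 2, Section 6.2.2 specifies the model as follows: "Using an intention-to-treat analysis, the proportion of concordant patients will be modeled using the logistic regression approach for binary outcome". The odds ratio and its test both come from the group coefficient of that model. On covariates, the section has two consecutive sentences: "To evaluate the success of randomization, we will test the differences in characteristics of physicians and patients between the two arms", followed by "The Logistic model will include statistically significant characteristics as covariates". Read together, the entry criterion is a significant difference between arms. The section sets a two-sided 0.05 level for all its tests.

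Nothing elsewhere fixes the Aim 2 set. The opening of Section 6.2 says only, of the survey and record data: "This information will be used to evaluate outcomes, predictors and adjust for covariates". Section 4.6 lists what is abstracted: "Covariate data will include sociodemographic information, cancer information, germline and somatic genomic biomarker testing, and dates and types of treatments for cancer". Age and education are named as examples in Sections 6.2.1 and 6.2.3, but for recall. Aim 1 also has an unadjusted chi-square test. Aim 2 has no named unadjusted or fixed-covariate main model, and the characteristics to be tested are not listed.

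**The concern.** In a randomised trial, a difference between arms in a characteristic fixed before allocation is, among all randomised patients, a chance event. A test of it has a 5% chance of significance, and that chance does not depend on whether the characteristic predicts the outcome. A covariate earns its place by predicting the outcome, so this criterion selects on the wrong property.

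Two things follow. A strongly prognostic characteristic is left out about 95% of the time, and the precision it could have given is lost. And because odds ratios are non-collapsible, a model with a prognostic covariate estimates a different conditional odds ratio from a model without it. Which one is reported is settled only when the arms are compared.

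Imbalance need not be pure chance among the patients who remain after dropout (Section 6.1: "We assume that there will be a 10% attrition rate among accrued patients") or for survey items answered after allocation. A significance test is no better guide to adjustment there.

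**Working it through.** **Inputs.** From the documents: two-sided 0.05 and the between-arm entry rule (Section 6.2.2); 130 vs 260 patients and 39% vs 54% (Section 6.2.1). The last four are Aim 1 recall figures. The documents give no Aim 2 sample size, concordance rate or power, so they are borrowed here. Assumed: ten independent standard-normal characteristics, two of them prognostic, at log-odds 0.3, 0.5 or 0.8 per SD (odds ratios 1.35, 1.65, 2.23).

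**1. The plan's own power figure (Aim 1).** Pooled proportion = (130×0.39 + 260×0.54)/390 = 0.49. Null SE = √[0.49×0.51×(1/130 + 1/260)] = 0.0537. Alternative SE = √[0.39×0.61/130 + 0.54×0.46/260] = 0.0528. Power = Φ[(0.15 − 1.96×0.0537)/0.0528] = 80.2%, against the stated 80%. It reproduces.

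**2. How often covariates enter.** Each enters with probability 0.05. At least one of 5, 10 or 20 independent characteristics enters with probability 1 − 0.95^k = 23%, 40% or 64%. Most of these entries are harmless, because a non-prognostic covariate barely changes the result. The relevant figure is entry of a prognostic one: 1 − 0.95² = 9.75%, and 9.6–10.1% in simulation.

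**3. Power.** The conditional log odds ratio is ln(0.54/0.46) − ln(0.39/0.61) = 0.608. The control log-odds are those of 0.39 at the covariate mean. Selection is by t-test at p < 0.05, and the treatment effect is tested by Wald test. There were 10,000 simulated trials per cell (Monte Carlo SE at most 0.5 points).

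| Model | 0.3 | 0.5 | 0.8 |
|---|---|---|---|
| Plan's rule | 77.1% | 71.0% | 61.3% |
| Unadjusted | 77.0% | 70.8% | 60.4% |
| Three prespecified, two prognostic | 78.8% | 75.5% | 71.1% |
| Three prespecified, one prognostic | 78.2% | 73.1% | 65.5% |
| Three prespecified, none prognostic | 77.0% | 70.9% | 60.9% |

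The gain over the rule is about 2, 5 and 10 points with two prognostic covariates, about 1, 2 and 4 with one, and nil with none. With no treatment effect, rejection rates were 4.4–5.7% across models.

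**4. With physician clustering.** Assumed: 30 physicians of 13 patients, intraclass correlation 0.05, small-sample-corrected robust standard errors, 4,000 trials per cell. Power under the rule is 72.0%, 65.8% and 56.2%; unadjusted 71.9%, 65.5% and 55.8%; prespecified with two prognostic 73.2%, 70.5% and 64.2%. The gains are about 1, 5 and 8 points.

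**5. Size of the estimand change.** Averaging the model over both prognostic covariates by numerical integration gives marginal odds ratios of 1.79, 1.73 and 1.62. Conditioning on one of the two gives about 1.81, 1.78 and 1.70–1.71. The odds ratio being estimated therefore shifts by about 1%, 3% and 5–6%, in the roughly 10% of trials where a prognostic covariate enters.

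**The case against.** The strongest reply is that the rule does little harm. It is written down in advance and does not use outcomes, so it gives no freedom to pick a favourable model. Type I error holds, power matches the unadjusted model, and Aim 2 is a secondary outcome. All of this stands and limits the severity.

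A reader might infer more than the documents support in three ways.

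- That selecting covariates on the data inflates the false-positive rate. It does not here: selection uses characteristics only, and the simulation shows no inflation.
- That the estimate becomes badly unstable. When a prognostic covariate enters, the estimated odds ratio moves by a median of 7%, 11% and 17%. Most of that is correction of chance imbalance, which is what adjustment is for. The change in the estimand is only the 1%, 3% and 5–6% above.
- That changed significance verdicts measure the damage. Under the rule, 1.8%, 2.7% and 4.0% of all trials differ from the unadjusted verdict. The prespecified model differs from it more often, in about 5–6%, 8–10% and 16%, so this is not a measure of harm.

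The power gain also rests on assumptions. Its upper end needs two well-chosen covariates with an odds ratio of 2.23 per SD. Section 6.2.2 assigns care benchmarks to patients with a pathogenic germline or actionable somatic variant, so the informative Aim 2 sample may not be 390.

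Finally, the binomial model that closes Section 6.2.2 and the linear-regression sensitivity analysis in Section 6.2.3 do not repeat the rule. Neither is named as the main estimate, so neither replaces it.

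**Conclusion.** The point holds in a limited form. Choosing Aim 2 covariates by between-arm significance brings almost none of the benefit of adjustment, and it leaves the reported conditional odds ratio dependent on chance imbalance. The forgone power is between nil and about 10 points, depending on how prognostic the available covariates are. These figures rest on Aim 1 rates and sample sizes and on an assumed set of ten characteristics with two prognostic; the documents supply none of these for Aim 2. There is no threat to Type I error or to the Aim 1 test. Severity is minor to moderate and confined to the secondary outcome. It is worth changing because a better method costs little and uses data already being collected.

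**What to change.** In Section 6.2.2, delete the sentence that admits statistically significant characteristics, and describe baseline balance of patients and physicians without tests. Before any arm-level data are examined, write in:

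- **A short covariate list**, expected to be prognostic and fixed before allocation, kept whatever the observed balance. Candidates are age (Section 6.2 lists "patient demographic information collected via the electronic medical record (EMR" among its data sources), education (Section 4.1.1), and cancer information from the medical record dated before enrolment (Section 4.6). Survey scores such as genomic knowledge qualify only if confirmed to precede allocation and the pamphlet, which Appendix I encloses with the baseline survey letter.
- **A rule for missing covariate values that ignores arm**, for example the overall mean, or a missing category for education, so that no patient leaves the intention-to-treat set.
- **The main estimate**: the adjusted odds ratio, labelled as conditional on the listed covariates, with the unadjusted one beside it.

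The cost is wording and a few degrees of freedom; no new data are needed. There is little or no gain if the covariates are weakly prognostic. The conditional odds ratio will differ from the unadjusted one (1.86, 1.85 and 1.86 against 1.80, 1.73 and 1.63 in the simulation with two of three prognostic), so both must be shown. The missing-value rule matters. If 5% or 10% of patients (assumed) lacked a covariate and were dropped, 390 would fall to about 370 or 351. Power for 39% vs 54% by the formula in step 1 would fall from 80.2% to 78.1% or 75.9%, which could cancel the gain.

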6.2.3 Exploratory Outcomes

Recall rates at 3-month: Recall rates of personal genomic results at the 3-month post-disclosure timepoint for Arms 2 and 3 of the study will be pooled together so that the main comparison is a two-

sample test of proportions between patients under usual care (Arm 1) vs. patients with any exposure to the HOPE-Genomics tool (Arms 2/3). Rates of recall will be analyzed using a two group Chi-Square test of equal proportions, and logistic regression when controlling for covariates such as age and education level. The overall fit of the model will be examined using Hosmer-Lemeshow goodness-of-fit test and ROC curves. If any normality issues arise, non-parametric techniques such as the Mann-Whitney test will be deployed.

Concordance Score: We will also use linear regression to conduct sensitivity analysis and test if the use of HOPE-Genomics will result in higher rates of uptake of evidence-based genetically-guided care (e.g., patient receipt of guideline concordant care, cascade testing) than usual care. The created summary concordance score of genetically-guided care variable ranging from 0-100% will be used to as numeric outcome. The null hypothesis is that the concordance score is not different between arms. We will consider two-sided p-value less than 0.05 as a statistically significant.

Test-related distress: We hypothesize that patients who view HOPE-Genomics will have lower test-related distress than patients in the usual care group: Patients will be assessed at 3 post-disclosure time points (T1-T3) using the PAGIS Certainty Scale and the FACToR. Some patients may have little test-related distress, whereas others may score higher (e.g., if testing reveals cancer or non-cancer related disease risk). Test-related distress is thought to decrease with time from the disclosure visit. We will summarize test-related distress at each time point, as well as change score. We will examine baseline characteristics to evaluate the potential for bias. In addition to complete case analysis, sensitivity analyses (e.g., using weighted methods) may occur to evaluate bias. We will use clustered Wilcoxon test for mean score comparison between groups at each time point. In addition, mean change in score from T1 to T3 will be modeled using GEE model adjusting for patient characteristics. We will use Autoregressive (AR1) and compound symmetry working correlation matrix to account for repeated measurement correlation and within-physician correlation. The significance of the coefficient will be tested to determine difference between two groups.

General genomic knowledge: We hypothesize that patients in the Return of Results plus Pre-test Education (Arm 3) arm will have better general genomic knowledge than the Return of Results only and Usual Care arms (Arms 1/2). To examine this, we will compare the pre/post test scores between the intervention group (Arm 3) and the control groups (Arms 1/2). The pre/post test scores will be calculated by taking the difference in score between pre/post tests and then comparing the mean differences with an independent T-test between control groups (Arms 1/2) versus the exclusive exposure to the HOPE-Genomics tool educational content (Arm 3). We also hypothesize that Arm 3 will have better knowledge of the difference between germline and somatic testing, as measured in the modified Lung-MAP instrument, which has been adapted and implemented in our survey. We will test this difference as above, testing the mean difference in scores of the modified Lung-MAP instrument across Arms 1 and 2 vs Arm 3.

Genetically-guided care: In exploratory analyses related to Aim 2 (i.e. receipt of contextual guideline-concordant care), we will also operationalize the secondary outcome in an additional way: Categories of genetically-guided care: We will evaluate patients' receipt of 1) treatment recommended by provider based on sequencing (any/none), 2) patients' sharing of sequencing results with family members (any/none), and 3) patients' consultation with genetic counseling/ recommended specialist (any/none).

HOPE-Genomics tool usage: Finally, in order to understand how patients and physicians use HOPE-Genomics and to determine whether refinements are required prior to dissemination, we will analyze the web-log of user visits (e.g., number of viewing sessions, page views and use of interactive elements).

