Medical record abstraction (MRA); Post disclosure: 10 days (T1); 3 months (T2); 9 months (T3); Medications (Meds); Genetic counseling (GC); Physician (MD)

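### For the exploratory distress outcome, the 9-month between-group test uses complete cases with no committed correction, so drop-out linked to earlier distress differently by arm would bias it modestly

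*Combined protocol and SAP*

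**What the plan says.** The test-related distress paragraph in 6.2.3 (Exploratory Outcomes) sets out the schedule: "Patients will be assessed at 3 post-disclosure time points (T1-T3) using the PAGIS Certainty Scale and the FACToR". The footnote to Table 1 puts these visits at 10 days, 3 months and 9 months after disclosure.

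Two analyses follow. The first is per visit: "We will use clustered Wilcoxon test for mean score comparison between groups at each time point". The second is longitudinal: "mean change in score from T1 to T3 will be modeled using GEE model adjusting for patient characteristics", with AR1 and compound-symmetry working correlations named for the repeated measurements and for clustering within physician.

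On missing scores there are two sentences. One is a commitment to look: "We will examine baseline characteristics to evaluate the potential for bias". The other is optional: "In addition to complete case analysis, sensitivity analyses (e.g., using weighted methods) may occur to evaluate bias". No weighting model, variables or trigger is given, and section 6 has no other missing-data method for distress.

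On numbers, section 6.1 says "We expect to accrue 465 patients: 155 per each arm" and "We assume that there will be a 10% attrition rate among accrued patients, leaving us with a final analytical sample of 390 patients". No sample size, power or drop-out figure is given for distress itself.

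**The concern.** A patient who answers at 10 days and 3 months but not at 9 months contributes nothing to the 9-month Wilcoxon test, although two earlier scores are in hand. That test is safe if loss is unrelated to distress, or related to it in the same way and to the same extent in both groups. Otherwise the patients who remain differ between groups for a reason other than the tool.

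The error can go either way. Losing more of the distressed patients from the tool arms yields lower observed distress there, which is what the plan hypothesises. Losing them from usual care makes a harmless tool look harmful. Examining baseline characteristics can describe such an imbalance but does not remove it, and leaving the weighted analysis optional leaves room to choose after the data are seen.

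**Working it through.** **1. The plan's own figures.** For the primary outcome, 39% against 54% with 130 and 260 patients (two-sided 0.05, pooled variance, no continuity correction) gives 80.2% power, so N = 390 is reproduced. The attrition figures do not agree: 465 × 0.90 = 418.5, whereas 1 − 390/465 = 16.1%. Both rates are used below.

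**2. Assumed inputs.** These are not in the documents:
- no true group effect, and normal scores with SD 1;
- usual care (155) against the two tool arms pooled (155 + 155 = 310);
- correlations of 0.60 (T1-T2), 0.50 (T1-T3) and 0.65 (T2-T3);
- drop-out after T2, logistic in the T2 score, with log-odds 0.8 per SD in one group and none in the other;
- equal total loss in both groups, and no physician clustering.

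**3. Bias at T3.** Let s be the shift in the mean T2 score among those retained. Numerical integration of the logistic model over a standard normal gives s = −0.075 at 10% loss and −0.119 at 16.1%. The T3 mean of those retained moves by 0.65 × s:
- 10% loss: 0.65 × 0.075 = 0.049 SD
- 16.1% loss: 0.65 × 0.119 = 0.077 SD

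**4. False-positive rate.** With bias b and SE = √(1/n₁ + 1/n₂), the rate is Φ(b/SE − 1.96) + Φ(−b/SE − 1.96).
- 10% loss: n = 139.5 and 279, SE = 0.104, b/SE = 0.47, rate 7.6%
- 16.1% loss: n = 130 and 260, SE = 0.107, b/SE = 0.72, rate 11%

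Simulation agrees: about 7-8% and 11%, whether by t-test or by an unclustered Wilcoxon test. Reversing which group carries the link reverses the sign.

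**5. Milder links.** At 16.1% loss, a link of 0.4 gives s = −0.063. With 0.8 in one group and 0.4 in the other, b = 0.65 × (0.119 − 0.063) = 0.036 SD. The rate is 6.3% by the formula and about 6.5-7% in simulation. With equal links and equal loss the shifts cancel, and rejection is about 5%.

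**6. What is not affected.** Drop-out after T2 leaves the T1 and T2 comparisons intact. For the T1-T3 change, the T1 mean of those retained moves by 0.60 × s and the T3 mean by 0.65 × s, so the bias is (0.65 − 0.60) × 0.119 = 0.006 SD. That near-cancellation depends on the two correlations being similar. If the planned GEE instead takes all scores as repeated measures, simulated T3 bias was at most 0.015 SD.

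**7. A harsher mechanism.** If loss depends on distress at the missed visit itself, in one group only, with odds ratios of 1.5 to 3 per SD, the bias at 16.1% loss is 0.06-0.15 SD and the false-positive rate 9-29%. No analysis that assumes missing at random fully repairs this case.

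**The case against.** The strongest reply is that the plan already has a longitudinal model. AR1 and compound-symmetry structures only make sense with several scores per patient, so the GEE can be read as using every available score. On that reading it performs about as well as a mixed model under the assumptions above (rejection 4.8-5.5% at 16% and 25% loss). If it uses one change score per patient, its bias is about 0.01 SD or less. This stands, and it confines the problem to the per-visit test at the later visits. A reader might infer that the whole distress analysis is unsound; the documents do not support that.

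A reader might also infer that distressed patients will leave one arm more than another. Nothing in the protocol establishes it. Survey follow-up, contact attempts and gift cards are common to all arms (4.1.2, 4.4), and the extra calls to the tool arms concern tool viewing. The Appendix M script does end participation for patients left without tool access and says their information will be removed, a route usual care does not face during follow-up. That makes unequal loss possible, but it says nothing about distress.

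Nor is this the only psychosocial measure: HADS is collected at baseline and at each follow-up (4.1.1), although section 6.2 specifies no test for it. Finally, the plan expects some patients to report little distress, which suggests skewed scores and favours a rank test. That is a fair reason to keep the Wilcoxon test and to use robust standard errors in any model.

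**Conclusion.** The point holds in a limited form. The 9-month complete-case comparison of an exploratory outcome is open to bias if drop-out depends on earlier distress differently by arm, and no correction is committed to. Under the one-group link, the size is about 0.05 SD with a 7-8% false-positive rate at 10% loss, and about 0.08 SD with 11% at 16%. It is about 0.04 SD and 7% at 16% loss under the milder 0.8 against 0.4 link, and zero when links and loss rates are equal. All of this rests on assumed links and correlations.

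It does not reach the 10-day comparison, the 3-month comparison under drop-out after that visit, the T1-T3 change contrast, or the primary 10-day recall result. It is a worthwhile, inexpensive improvement and does not threaten the trial's main conclusion.

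**What to change.** In 6.2.3:
- Make the main between-group comparison at T2 and T3, for each instrument, a repeated-measures model using every available T1, T2 and T3 score. Either a linear mixed model with unstructured within-patient covariance, or the planned GEE stated explicitly to use all available scores, would serve.
- Include group, visit, group-by-visit and baseline predictors of drop-out already collected: HADS, self-rated health and performance status. Use robust standard errors for skewed scores and allow for physician clustering.
- Keep the complete-case clustered Wilcoxon test as a sensitivity analysis.
- Replace the optional weighting with a planned inverse-probability-weighted analysis, naming its variables.
- Tabulate losses, deaths and reasons by arm and visit.
- Reconcile the 10% attrition with the 390 analysed.

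The cost is SAP wording and one standard model on data already being collected. The model assumes missing at random. It cannot recover patients with no post-disclosure score or whose data are removed, and for patients who die the later score is hypothetical, which is why deaths should be shown beside it.
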